6.5.12 Safety assessments

The following safety events will be collected in this study, providing the below details have confirmed that they qualify:

- Serious Adverse Events (SAEs)
- Non-serious AEs assessed as causally related to treatment with rFVIIIFc or rFIXFc and considered unexpected
- AEs of special interest: inhibitor development, thrombotic events and serious hypersensitivity reaction including anaphylactic reactions
- AEs leading to premature discontinuation of rFVIIIFc or rFIXFc
- Exposure during pregnancy, medication errors, misuse or abuse in relation to rFVIIIFc or rFIXFc

Medication error is defined as an unintended failure in the study treatment process that leads to, or has the potential to lead to, harm to the patient; misuse is defined as situations where the study treatment is intentionally and inappropriately used not in accordance with the terms of the clinical study protocol; and abuse is defined as persistent or sporadic, intentional excessive use of study treatment by a study patient accompanied by harmful physical and/or psychological effects.

Any AE suspected to be causally related to a medicinal product other than the studied Sobi products, and which does not result from a possible interaction with it, should be reported by the Investigator to the concerned authority via the national reporting system, or to the Marketing Authorization Holder of the suspected medicinal product.

Sobi

Eftrenonacog alfa/Alprolix® - Efmorocog alfa/Elocta®Clinical Study No: Sobi.HAEM89-007**6.5.12.1 Adverse events****6.5.12.1.1 Definitions**

An AE is any untoward medical occurrence in a study patient to whom a medicinal product is administered and which does not necessarily have a causal relationship with this treatment.

AEs include the following:

- Abnormal test findings, as specified below
- Clinically significant signs and symptoms
- Changes in physical examination findings
- Progression/worsening of underlying disease

In addition, signs and symptoms resulting from the following should also be handled according to the same principles as AEs:

- Overdose
- Withdrawal of treatment
- Interactions

In order to qualify for reporting as an AE in this study, at least one of the above-mentioned criteria must be met, and be in accordance with the listed safety data to be collected as defined at the beginning of this section.

For pregnancies and breastfeeding, see section 6.5.12.14.

6.5.12.2 Abnormal test findings, pre-existing conditions, procedures

Any abnormal test finding or pre-existing condition, which worsens or increases in frequency or any unplanned medical procedures should be recorded, if any of the following criteria apply:

- SAEs
- Non-serious AEs assessed as causally related to treatment with rFVIIIFc or rFIXFc and considered unexpected
- AEs of special interest: Inhibitor development, thrombotic events and serious hypersensitivity reaction including anaphylactic reactions
- AEs leading to premature discontinuation of rFVIIIFc or rFIXFc
- Exposure during pregnancy, medication errors, misuse or abuse in relation to rFVIIIFc or rFIXFc

Diagnostic and therapeutic non-invasive and planned invasive procedures, such as planned surgery, should not be reported as AEs.

Sobi

Eftrenonacog alfa/Alprolix® - Efmorocog alfa/Elocta®

Clinical Study No: Sobi.HAEM89-007

6.5.12.3 Lack of efficacy

Failure of pharmacologic action or therapeutic benefit shall be recorded only when assessed as an SAE.

6.5.12.4 Serious adverse event

An AE that meets one or more of the following criteria/outcomes is classified as serious:

- Results in death.
- Is life threatening (i.e., at immediate risk of death).
- Requires in-patient hospitalization or prolongation of existing hospitalization.
- Results in persistent or significant disability/incapacity.
- Is a congenital anomaly/birth defect (i.e., in an offspring to the study patient).
- Is a medically important AE.

Medically important AEs are events that may not result in death, be life threatening, or require hospitalization but may be considered serious when, based upon appropriate medical judgement, may jeopardize the patient or may require medical or surgical intervention to prevent one of the outcomes listed above. Examples of such events are intensive treatment in an emergency room or at home for allergic bronchospasm, blood dyscrasias or convulsions that do not result in hospitalization or development of dependency or abuse.

Serious also includes any other event that the investigator or company judges to be serious. Any suspected transmission via a medicinal product of an infectious agent is also considered serious.

6.5.12.5 Hospitalization

Hospitalization includes transfers within a hospital (e.g. from the psychiatric unit to the intensive care unit) and also includes admissions less than 24 hours. The following situations are not considered hospitalizations (although other SAE criteria may still apply):

- Outpatient procedures/ambulatory care
- Emergency department visits

Hospitalization in the absence of an AE occurring during the study should not be considered an SAE. This includes:

- Hospitalization due to a pre-existing condition not associated with a worsening of the pre-existing condition
- Protocol-specified admission
- Elective admission, e.g. due to cosmetic surgery
- Pre-planned admission for a condition specified at baseline for the patient

6.5.12.6 Suspected Unexpected Serious Adverse Reaction (SUSAR)

A SUSAR is an adverse reaction which is not consistent with the EU SmPC.

Sobi

Eftrenonacog alfa/Alprolix® - Efmorocog alfa/Elocta®

Clinical Study No: Sobi.HAEM89-007

6.5.12.7 Adverse event reporting period

The period for recording all AEs in the eCRF begins upon signature of the informed consent form and collection of non-serious AEs ends at the last study visit.

All SAEs should be reported to Sobi from the time the patient has signed the informed consent until the EOS visit. Subsequently only SAEs assessed by the investigator as related, and fatal SAEs, should be reported during the follow-up period, until EOS visit.

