6.1 Overall study design and plan

This is a prospective, low-interventional, single-arm, multicentre study to describe the joint health over an 18-month period of prophylactic treatment with rFVIIIFc or rFIXFc in patients with haemophilia A or haemophilia B in a real-world setting. Approximately 250 patients will be enrolled in the study. Around 80% of the patients are expected to have haemophilia A and around 20% haemophilia B.

Retrospective data from patient medical records will be collected for at least 6 months before enrolment in the study. From enrolment and throughout the study, patients will perform on-site study visits at 6-month intervals. Each patient is expected to actively participate in the study for 18 months (from baseline to end of study [EOS] visit).

Joint health will be assessed with HEAD-US and HJHS scoring. Quality of life and physical activity will be assessed with PROs. Patients will be on prophylactic treatment with rFVIIIFc or rFIXFc according to usual clinical practice and the dosing guide in the respective Summary of Product Characteristics (SmPC). Choice of treatment will not be dictated by the study protocol.

The recruitment period is planned to be approximately 12 months from the timepoint when the first patient is enrolled in the study. Around 60 sites in approximately 11 European countries are expected to participate in the study.

No specific evaluation committees will be utilized for this study, since it is a low-interventional study having no interventions posing more than minimal risk to the patients.

Interim analyses are planned to be performed during the study. The first interim analysis is to be performed once recruitment is completed. The purpose of the first interim analysis is to assess the baseline variability of HEAD-US score results and to share baseline characteristics with the haemophilia community. The second interim analysis is planned to be performed once at least 50% of the patients have completed their 12-month visit and will evaluate the joint health status at that time.

In an optional, exploratory sub-study, data will be collected via the florio HAEMO app. All exploratory endpoints and objectives in the study are related to the exploratory sub-study.

[figure not shown]
The overall study design is described in Figure 1.

Sobi

Eftrenonacog alfa/Alprolix® - Efmorocog alfa/Elocta®

Clinical Study No: Sobi.HAEM89-007

Figure 1 Study Design

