6.2 Discussion of study design, including the choice of control groups

This prospective, low-interventional, multicentre study is being conducted to describe the joint health over an 18-month period in patients on prophylactic treatment with rFVIIIFc or rFIXFc with haemophilia A or haemophilia B in a real-world setting. The 18-month follow-up period is considered to be long enough to see changes and/or show medium/long-term stabilization of joint status. Patients treated on demand are not included in the study, as this would lead to a too high variability in the patient population.

Joint outcomes will be described over time and reported in a quantitative/objective manner with HEAD-US and HJHS scores. These assessments are not always fully incorporated in routine clinical practice and are therefore intended to be investigated in the low-interventional setting of this study. Both examinations have been chosen due to their complimentary features – HJHS is a clinical assessment focused on functionality and HEAD-US is a more sensitive US assessment with the ability to detect structural joint damage and synovitis earlier on in the joint deterioration.

This study will not have a control group. The reason for this is that it is not considered needed to be able to evaluate the primary objective of the study.

Patients excluded from participation in this study (section 6.3.2) will have been assessed as not being suitable for the study.

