6.3.3 Withdrawal of patients from study

6.3.3.1 Withdrawal from study

Whenever possible and irrespective of the reason for withdrawal, the patient should be examined as soon as possible. All relevant assessments should be completed, preferably according to the schedule of events (see section 6.5.1.1). The Case report form (CRF) should be completed as far as possible. Date and reason for the study withdrawal should be clearly described in the CRF.

A patient should be withdrawn from the study for any one of the following reasons:

- The patient develops factor VIII or FIX inhibitory antibodies (inhibitor titre ≥ 0.60 BU/mL)
- The patient or his legally authorized representative(s) withdraws consent
- The patient enrolls into an interventional clinical study in which an investigational treatment or approved therapy for investigational use is administered
- The patient enrolls into a low-interventional clinical study where the assessments performed are of such nature that the patient cannot be considered treated per usual routine practice
- The patient discontinues prophylactic treatment with rFVIIIFc or rFIXFc
- The patient is no longer willing to undergo the mandatory US examination

If any Adverse Event (AE) is associated with the withdrawal this should be recorded in the CRF.

If the patient withdraws consent for disclosure of future information (data, samples), the sponsor may retain and continue to use any data collected before such a withdrawal of consent.

Patients will not be withdrawn if they miss a study visit.

If a patient withdraws from the study and more than 3 months since the last study visit have passed, all assessments should be performed to the extent possible. If a patient withdraws from the study less than 3 months since the last visit, PRO collection and HJHS assessment should be performed to the extent possible.

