6.5.1.5 Visit 4 – Month 18/End of study

Data will be collected in accordance with the schedule of events (see section 6.5.1.1).

All study assessments should be performed within a -28 and +56 days time window. The date of the last assessment should be considered as the EOS date.

If a patient prematurely withdraws from the study and more than 3 months since the last study visit have passed, all assessments should be performed to the extent possible. If a patient withdraws from the study less than 3 months since the last visit, PRO collection and HJHS assessment should be performed to the extent possible.

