9.7 Data protection

Study patients will be assigned a unique identifier by the sponsor. Any patient records or datasets that are transferred to the sponsor will contain the identifier only; patient names or any information which would make the patient identifiable will not be transferred.

The patient must be informed that his/her personal study-related data will be used by the sponsor in accordance with local data protection law. The level of disclosure must also be explained to the patient who will be required to give consent for their data to be used as described in the informed consent.

The patient must be informed that his/her medical records may be examined by Clinical Quality Assurance auditors or other authorized personnel appointed by the sponsor, by appropriate IECmembers, and by inspectors from regulatory authorities.

The contract between sponsor and study sites specifies responsibilities of the parties related data protection, including handling of data security breaches and respective communication and cooperation of the parties.

Information technology systems used to collect, process, and store study-related data are secured by technical and organizational security measures designed to protect such data against accidental or unlawful loss, alteration, or unauthorized disclosure or access.

10 End of study

The end of this study is defined as the date of last patient out, i.e., the last patient's last visit.

11 Sponsor's discontinuation criteria

Sobi reserves the right to discontinue the study prior to inclusion of the intended number of patients but intends only to exercise this right for valid scientific or administrative reasons. After such a decision, the investigator must contact all participating patients before the next scheduled site visit. All study materials must be collected and all the CRFs completed to the greatest extent possible.

12 Dissemination and publication of results

Sobi will register the study by posting study information and post study results regardless of outcome on a publicly accessible website in accordance with applicable laws and regulations, e.g., on www.clinicaltrials.gov and EudraCT. The results of this study will be published within 6 months of the EOS.

Sobi

Eftrenonacog alfa/Alprolix® - Efmorocog alfa/Elocta®

Clinical Study No: Sobi.HAEM89-007

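### Does the second SAE sentence in section 6.5.12.7 leave the reporting of serious adverse events undefined?

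*Combined protocol and SAP*

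**What the plan says.** Section 6.5.12.7 has two consecutive sentences on SAEs. The first is "All SAEs should be reported to Sobi from the time the patient has signed the informed consent until the EOS visit". The second is "Subsequently only SAEs assessed by the investigator as related, and fatal SAEs, should be reported during the follow-up period, until EOS visit".

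The EOS visit belongs to the individual patient. Section 6.1 has each patient take part from baseline to the EOS visit, over 18 months. The schedule in 6.5.1.1 shows it as Visit 4, Month 18, the last column. Section 6.5.1.5 fixes its date: "The date of the last assessment should be considered as the EOS date". The end of the whole study is defined separately in section 10: "The end of this study is defined as the date of last patient out".

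No section defines a follow-up period after EOS. Where follow-up is used for a span of time, it means time in the study. Section 6.2 says "The 18-month follow-up period is considered to be long enough", and the schedule groups Months 6, 12 and 18 as follow-up visits.

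**The concern.** A rule that begins after an event cannot also end at that event. The sentence limiting reports to related and fatal SAEs is therefore either empty or, if follow-up means time in the study, a contradiction of the sentence before it.

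This section sets the SAE reporting period for around 60 sites in about 11 countries. On the restrictive reading, a site could leave out unrelated non-fatal SAEs during the 18 months, and the safety tables would be incomplete. On the other reading, if the sponsor meant related and fatal SAEs to be reported after Month 18, the sentence does not achieve it, because it gives neither an end point nor a route for such reports.

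**Working it through.** The plan has no figure to reproduce here. The check compares reporting windows and asks what each possible reading does to a site's duty.

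**Step 1. What each place requires.**

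| Place | Which SAEs | Period |
|---|---|---|
| 6.5.12.7, first SAE sentence | all | consent to EOS visit |
| 6.5.1.1, SAE row | SAEs, no restriction | marked in 5 of 5 visit columns |
| 6.5.1.1, footnote 8 | all, including medically important events | enrolment visit to the patient's last study visit |
| 6.5.12.12 | all, related or not, within 24 hours of awareness | no separate period given |
| 6.5.12.7, second SAE sentence | related and fatal only | after the first rule, to EOS visit |

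The first four rows agree with one another. Only the last stands apart.

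**Step 2. The readings of the second sentence.**

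- *Sequential, the natural one.* The rule starts when the first rule ends, at the EOS visit, and stops at the EOS visit. Length: EOS visit minus EOS visit = 0 days. No duty changes.
- *Follow-up as time in the study.* The window is the 18 months, all of it inside the first rule. The sentence then contradicts the first four rows of the table. It also leaves the word *subsequently* without meaning, so this reading is the less likely one.
- *A phase off treatment before EOS.* This does not fit. Section 6.3.3.1 lists as a reason for withdrawal from the study: "The patient discontinues prophylactic treatment with rFVIIIFc or rFIXFc".
- *The time from early withdrawal to the planned Month 18.* This is not written anywhere. Section 6.5.1.5 deals with the assessments at withdrawal under the EOS visit itself.
- *The study-level end in section 10.* This would give a real window. Section 6.1 says "The recruitment period is planned to be approximately 12 months", so on nominal dates the first patient's Visit 4 falls at month 18 and the last patient's at month 12 + 18 = 30. The window would be 30 − 18 = 12 months for the first patient and 0 for the last. Visit windows, the 28 days allowed between enrolment and baseline, and early withdrawal could lengthen it, so 12 months is not an upper bound. The reading is weak in any case, because section 10 does not call that date an EOS visit.

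**Step 3. What is said about time after participation.** Section 6.5.12.13 asks that related events, serious or not, be followed until resolved, chronic or stable even after the patient has left the study, without further eCRF entries. Section 6.5.12.12 makes the eCRF the route for SAE reports, with paper only if it is not functioning. Together with the end points in footnote 8 and the first SAE sentence, this points to no collection of new SAEs after EOS, although nothing expressly rules it out.

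**Step 4. Effect on the analysis.** Section 8.3.6.1 tabulates events reported during the study. Under the sequential reading these tables contain every in-study SAE. The primary analysis (8.3.3) and the precision table (8.1) use HEAD-US scores and no SAE data.

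**The case for a change.** The strongest case for acting is that the sentence looks like the remnant of a real intention. It names a class of events and a period. In addition, the opening sentence of 6.5.12.7 ends only the non-serious events at the last study visit, which suggests that SAE reporting was once meant to run longer. If so, a site that learns of a related or fatal SAE after Month 18 has no usable instruction, and 6.5.12.13 does not help, because it concerns events already reported. The repair would cost one sentence and a short note to sites.

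Part of this stands. The wording is defective, the sponsor's intention after EOS cannot be recovered from the text, and 6.5.12.7 does not sit cleanly with footnote 8, 6.5.12.12 and 6.5.12.13. What does not stand is that the reporting rule cannot be applied. That is true of the second sentence alone. The first sentence, the schedule row, footnote 8 and 6.5.12.12 give sites a complete duty for the whole of each patient's participation. A site would have to set all four aside to under-report during the study.

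**Conclusion.** A clerical slip that calls for no change to the plan. On the natural reading the second sentence governs 0 days and alters nothing. On the less likely reading it is outweighed by four consistent statements elsewhere. A site following the plan reports all in-study SAEs, and the safety tables, the HEAD-US estimate and its precision are as they would be without the sentence.

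This rests on two assumptions: that sites take the EOS visit to be the patient's own Visit 4, as 6.1, 6.5.1.1 and 6.5.1.5 do, and that they follow the repeated all-SAE instruction over a single sentence that cannot be squared with it. What the sponsor intended for new SAEs after EOS remains unstated. Settling it would be an editorial clarification and is not shown to change any result or conclusion of this study.

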6.5.12.8 Obtaining and recording adverse event information

The investigator is to record all observed AEs (directly observed, spontaneously reported by the patient or solicited), in the eCRF using concise medical terminology.

Each patient will be questioned about AEs at each clinic visit following initiation of treatment. The question asked will be “Since your last clinic visit, have you had any health problems?”.

When possible and appropriate, a diagnosis rather than individual signs and symptoms shall be recorded. The investigator is responsible for obtaining sufficient information to determine seriousness, causality and outcome of each AE.

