8.3.6 Analysis of safety and tolerability data

8.3.6.1 Adverse events

Reported AEs during the study will be coded using the Medical Dictionary for Regulatory Activities. The incidence of AEs will be summarized in frequency tables by treatment, system organ class, preferred term and maximum severity. Separate tabulations will be performed for serious and non-serious AEs.

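### Adverse event recording is restricted to a list in 6.5.12 but unrestricted in 6.5.12.7 and 6.5.12.8, and the non-serious and overall AE tables in 8.3.6.1 would not estimate incidence

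*Combined protocol and SAP*

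**What the plan says.** **Restricted rule.** Section 6.5.12 (and the synopsis, under Assessments) lists what is collected:

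- every SAE;
- events of special interest, meaning inhibitors, thrombosis and serious hypersensitivity;
- events that lead to the product being discontinued;
- pregnancy exposure, medication error, misuse or abuse;
- of the remaining non-serious events, only this group: "Non-serious AEs assessed as causally related to treatment with rFVIIIFc or rFIXFc and considered unexpected".

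Section 6.5.12.1.1 makes the list a condition of reporting: besides meeting the AE definition, an event must "be in accordance with the listed safety data to be collected as defined at the beginning of this section". Section 6.5.12.2 applies the same list to abnormal findings and pre-existing conditions, which "should be recorded, if any of the following criteria apply". Under 6.5.12.3, lack of efficacy "shall be recorded only when assessed as an SAE".

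**Unrestricted rule.** Section 6.5.12.8 states: "The investigator is to record all observed AEs (directly observed, spontaneously reported by the patient or solicited), in the eCRF". The question put at each visit is open: "Since your last clinic visit, have you had any health problems". Section 6.5.12.7 says: "The period for recording all AEs in the eCRF begins upon signature of the informed consent form". Section 6.5.12.12 sends serious and non-serious AEs alike to the AE page and leaves the detail to eCRF instructions, which are not among the documents. None of these three sections refers back to the list.

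**Analysis.** Section 8.3.6.1 summarises AE incidence by treatment, system organ class, preferred term and maximum severity. It adds: "Separate tabulations will be performed for serious and non-serious AEs". It does not say that only listed categories are counted, and it names no table for AEs of special interest or AEs leading to discontinuation.

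**The concern.** There are two issues.

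The first is the recording rule. Around 60 sites in about 11 countries must decide what to enter. Read literally, 6.5.12.8 brings in every minor complaint that the visit question elicits; read literally, 6.5.12.1.1 keeps most of them out. If sites resolved this differently, the non-serious counts would partly reflect which section a site followed.

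The second is the table, and it remains when every site follows the list. An incidence needs every occurrence of the event in the numerator. Here a non-serious event enters only after passing a filter on relatedness and expectedness, or by another listed route. A low or zero count for a preferred term could then mean that the event was rare, or that it occurred and was not collectable. A reader of a table titled incidence of AEs could not tell which.

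**Working it through.** The plan states no AE rate, so there is no figure to reproduce. The check sets the two rules side by side by type of event.

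| Event | List in 6.5.12 | 6.5.12.8 read literally |
|---|---|---|
| SAE | recorded | recorded |
| AE of special interest | recorded | recorded |
| AE leading to discontinuation | recorded | recorded |
| Non-serious, related, unexpected | recorded | recorded |
| AE with pregnancy exposure, medication error, misuse or abuse | recorded | recorded |
| Non-serious, related, expected, in no other listed category | not recorded | recorded |
| Non-serious, unrelated, in no other listed category | not recorded | recorded |

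1. The rules differ only in the last two rows. The SAE table is the same under both, and 6.5.12.12 separately requires every SAE to be recorded whatever its relation to treatment.
2. Those two rows feed the overall and non-serious tables in 8.3.6.1, with their breakdowns by system organ class, preferred term and severity.
3. If all sites apply the list, both rows are empty by design. The proportion reported for a preferred term is then the proportion of patients with that event *and* a qualifying route. It can be no larger than the true incidence, and the gap is unknown.
4. If sites differ, let s be the share of patients at sites that record everything, a the probability of at least one qualifying AE, and b the probability of at least one AE of any kind. The pooled proportion is p = s × b + (1 − s) × a. It lies anywhere between a and b, according to s.
5. The table would be an ordinary incidence only at s = 1, that is, if every site disregarded the list.

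To show how the formula in step 4 behaves, here are values that are **assumed**, not taken from the documents:

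| a | b | s = 0 | s = 0.5 | s = 1 |
|---|---|---|---|---|
| 10% | 40% | 10% | 0.5 × 40% + 0.5 × 10% = 25% | 40% |
| 15% | 60% | 15% | 0.5 × 60% + 0.5 × 15% = 37.5% | 60% |
| 10% | 80% | 10% | 0.5 × 80% + 0.5 × 10% = 45% | 80% |

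The rows show only that p depends on s. They are not evidence that s lies strictly between 0 and 1 in this study.

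**The case against.** The best answer is that the plan already states a governing rule. Section 6.5.12.1.1 defines what qualifies for reporting, and 6.5.12.7 and 6.5.12.8 are later parts of the same section. Footnote 7 to the schedule of events points to the safety section for what is to be captured, and 8.3.6.1 speaks of AEs that were reported. Section 6.5.12.8 can be read as describing how events come to light, since its parenthesis lists sources. An open question is needed under a restricted list too, because seriousness, causality and expectedness can be judged only once an event is known. EDC user training, edit checks, monitoring and the eCRF instructions may also keep sites aligned. Restricted collection is a deliberate choice, defended in 6.5.12.15, and the study has no safety objective or endpoint.

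Most of this stands. It makes divergence between sites a risk and not a finding. It does not repair the tables: the reading that reconciles the sections is the one in which the non-serious counts are filtered.

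A reader might also infer four stronger things that the documents do not support.

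- *That related events already in the SmPC are never recorded.* They are, if serious, of special interest, leading to discontinuation or otherwise listed.
- *That sites do differ, or that the reported rate would shift by some stated amount.* No rate and no information on site practice is given; about 60 sites and about 250 patients show neither.
- *That the error favours the products.* The filter lowers counts and over-recording raises them, so the net direction is undetermined.
- *That events of special interest are lost from view.* Preferred-term tables would show them; inhibitor development requires withdrawal under 6.3.3.1, and 8.3.2 summarises withdrawal reasons. The SAP promised in 8.3.1 may add dedicated tables, although 8.3.6.1 does not commit to them.

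**Conclusion.** The concern holds as a conflict of wording combined with a mislabelled analysis. The recording sections do not agree on their face and should be reconciled; whether sites would act differently is not known. Whether sites follow the list uniformly or vary, the overall and non-serious tables in 8.3.6.1 do not estimate AE incidence.

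The size cannot be given, because it depends on AE rates and site practice that the documents do not contain. The scope can be: the overall and non-serious tables and their breakdowns. The SAE table, the collection of AEs of special interest and of AEs leading to discontinuation, the primary endpoint and the sample size are unaffected. The conclusion rests on the current text alone; eCRF instructions that restate the list would reduce the risk of divergence but would leave the labelling problem.

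**What to change.** **Recording.** In 6.5.12.7, 6.5.12.8 and 6.5.12.12, qualify each reference to AEs with *that qualify under section 6.5.12*, and align the eCRF instructions. The open visit question can stay as the means of finding events.

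**Tables.** In 8.3.6.1, tabulate by collected category:

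1. SAEs;
2. AEs of special interest, by type;
3. AEs leading to discontinuation;
4. related and unexpected non-serious AEs;
5. medication errors, misuse, abuse and pregnancy exposure.

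An overall or non-serious table may be kept if its title and footnote say that it covers only the collected categories.

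**Statement.** Say in 8.3.6.1 and in the report that other non-serious AEs were not systematically collected, so their incidence is not estimated.

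**Cost.** Protocol and eCRF-instruction wording plus table shells; no added visits, assessments or patients. The price is that no general any-AE incidence can be quoted.
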